### 9.3.1 ADA subject classification

All available ADA assay results (positive or negative) per subject will be evaluated and subjects will be classified based on a combined statement on pre-Ab status (pre-Ab neg or pre-Ab pos, to be derived from parent trial) and the TE ADA response (TE neg, TE pos, Equivocal (EQ) or inconclusive) as outlined in [Table 2](#).

For each subject, one ADA subject classification will be determined. This implies that in the listing subject classification will be identical for all ADA visits of the given subject.

**Table 2: ADA subject classification**

ADA subject class	Evaluation based on all ADA assay results (titer) of the respective subject	
	Pre-Ab status evaluated on screening and baseline sample of parent trial	TE ADA Response evaluated based on Week 12, Week 24, Week 36, Week 48, Week 60, Week 72, Week 84, Week 96, Week 104 and FU or ET visit
PRE-AB NEG - TE ADA NEG	All pre-dose samples negative	All post-dose samples ADA negative
PRE-AB NEG - TE ADA POS	All pre-dose samples negative	At least one positive ADA sample(s) post-dose
PRE-AB NEG - TE ADA INCONCLUSIVE	All pre-dose samples negative	All post-dose samples(/results) are missing
PRE-AB POS - TE ADA NEG	One or more of the pre-dose samples is positive	All post-dose samples are ADA negative
PRE-AB POS - TE ADA POS	One or more of the pre-dose samples is positive	Significant increase in titer post-dose versus pre-dose*
PRE-AB POS - EQ	One or more of the pre-dose samples is positive	Positive ADA sample(s) post-dose and no significant increase in titer post-dose versus pre-dose*
PRE-AB POS - TE ADA INCONCLUSIVE	One or more of the pre-dose samples is positive	All post-dose samples(/results) are missing
MISSING	No pre-dose samples are available	N/A

\* The titer is considered to be significantly increased post-dose, if the highest post-dose titer compared to the highest pre-dose titer is higher than the ADA MSR value: the increase of the  $\log_{10}(\text{titer})$  post- versus pre-dose should be  $> \log_{10}(\text{MSR})$ .

### 9.3.2 mADA subject classification

All available mADA assay results (positive or negative) per subject will be evaluated and subjects will be classified based on a combined statement on pre-Ab status (pre-Ab neg or pre-Ab pos, to be derived from parent trial) and the TE ADA response (TE neg, TE pos, EQ or inconclusive) as outlined in Table 3.

For each subject tested in the mADA assay (i.e. "PRE-AB POS - EQ" subjects based on ADA assessment), one mADA subject classification will be determined. This implies that in the listing this will be identical for all ADA visits of the given subject. In case the subject was not tested in the mADA assay, corresponding fields in the listing will remain empty.

**Table 3: mADA subject classification**

mADA subject class	Evaluation based on all mADA assay results (titer) of the respective subject	
	Pre-Ab status evaluated on screening and baseline of parent trial	TE ADA Response evaluated based on Week 12, Week 24, Week 36, Week 48, Week 60, Week 72, Week 84, Week 96, Week 104 and FU or ET visit
PRE-AB NEG - TE ADA NEG	All pre-dose samples negative	All post-dose samples ADA negative
PRE-AB NEG - TE ADA POS	All pre-dose samples negative	At least one positive ADA sample(s) post-dose
PRE-AB NEG - TE ADA INCONCLUSIVE	All pre-dose samples negative	All post-dose samples(/results) are missing

PRE-AB POS - TE ADA NEG	One or more of the pre-dose samples is positive	All post-dose samples ADA negative
PRE-AB POS - TE ADA POS	One or more of the pre-dose samples is positive	Significant increase in titer post-dose versus pre-dose*
PRE-AB POS - EQ	One or more of the pre-dose samples is positive	Positive ADA sample(s) post-dose and no significant increase in titer post-dose versus pre-dose*
PRE-AB POS - TE ADA INCONCLUSIVE	One or more of the pre-dose samples is positive	All post-dose samples(/results) are missing
MISSING	No pre-dose samples are available	N/A

\* The titer is considered to be significantly increased post-dose, if the highest post-dose titer compared to the highest pre-dose titer is higher than the mADA MSR value: the increase of the  $\log_{10}(\text{titer})$  post- versus pre-dose should be  $> \log_{10}(\text{MSR})$ .

### 9.3.3 Overall subject classification

Overall subject classification will be determined based on the combined results of ADA and/or mADA analysis. The classification is identical to the ADA subject classification, except for subjects classified as "pre-Ab pos - EQ" based on ADA assay results which are further evaluated in the mADA assay. For those subjects, a re-classification is done based on combined ADA and mADA assay. This is illustrated in [Table 4](#). For each subject, one overall subject classification is to be assigned. This implies that in the listing the overall subject classification will be identical for all ADA visits of the given subject.

**Table 4: ADA, mADA and Overall subject classification**

ADA subject classification	mADA subject classification	Overall subject classification
Missing	-	Missing
PRE-AB NEG - TE ADA NEG	-	PRE-AB NEG - TE ADA NEG
PRE-AB NEG - TE ADA POS	-	PRE-AB NEG - TE ADA POS
PRE-AB NEG - TE ADA INCONCLUSIVE	-	PRE-AB NEG - TE ADA INCONCLUSIVE
PRE-AB POS - TE ADA NEG	-	PRE-AB POS - TE ADA NEG
PRE-AB POS - TE ADA POS	-	PRE-AB POS - TE ADA POS
PRE-AB POS - TE ADA INCONCLUSIVE	-	PRE-AB POS - TE ADA INCONCLUSIVE
PRE-AB POS - EQ	Missing	PRE-AB POS - EQ
	PRE-AB NEG - TE ADA NEG	PRE-AB POS - EQ
	PRE-AB NEG - TE ADA POS	PRE-AB POS - TE ADA POS
	PRE-AB NEG - TE ADA INCONCLUSIVE	PRE-AB POS - EQ
	PRE-AB POS - TE ADA POS	PRE-AB POS - TE ADA POS
	PRE-AB POS - TE ADA INCONCLUSIVE	PRE-AB POS - EQ
	PRE-AB POS - TE ADA NEG	PRE-AB POS - EQ
	PRE-AB POS - EQ	PRE-AB POS - EQ

### 9.3.4 NAb subject class

All available NAb assay results (\*) (positive or (imputed) negative) per subject will be evaluated and subjects will be classified based on a combined statement on pre-dose status (pre-dose neg or pre-dose pos, to be derived from parent trial) and the post-dose response (negative, positive or inconclusive) as outlined in [Table 5](#).

(\*) Note that for the pre-dose Nab results (screening and baseline) from the parent trials (ALX0061-C201 or ALX0061-C202) 'Y' (Yes) should be imputed to POS and 'N' (No) should be imputed to NEG.

For each subject, one NAb subject classification is to be determined. This implies that in the listing this will be identical for all NAb visits of the given subject. For subjects with no positive ADA samples, the NAb results were imputed as "NEG\*", and the NAb subject class will be "PRE-DOSE NEG - NEG ON TREATMENT". The latter also has to appear in the Listing.

**Table 5: NAb subject classification**

NAb subject class	Evaluation based on all NAb assay results (titer) of the respective subject	
	Pre-dose status evaluated on screening and baseline of parent trial	Response on treatment evaluated based on Week 12, Week 24, Week 36, Week 48, Week 60, Week 72, Week 84, Week 96, Week 104 and FU or ET visit
PRE-DOSE NEG - NEG ON TREATMENT	All pre-dose samples negative (reported or imputed)	All post-dose samples are negative (reported or imputed)
PRE-DOSE NEG - POS ON TREATMENT	All pre-dose samples negative (reported or imputed)	At least one positive sample(s) post-dose
PRE-DOSE POS - NEG ON TREATMENT	One or more of the pre-dose samples is positive	All post-dose samples are negative (reported or imputed)
PRE-DOSE POS - POS ON TREATMENT	One or more of the pre-dose samples is positive	At least one positive sample(s) post-dose
PRE-DOSE NEG - INCONCLUSIVE	All pre-dose samples negative (reported or imputed)	All post-dose samples(/results) are missing
PRE-DOSE POS - INCONCLUSIVE	One or more of the pre-dose samples is positive	All post-dose samples(/results) are missing
MISSING	No pre-dose (and/or post-dose) samples are available	No pre-dose (and/or post-dose) samples are available

## 9.4 Pre-Ab prevalence and TE ADA Incidence calculations

### 9.4.1 Incidence of ADA and derived sets

The following subject categories (1-8) and derived sets (9-15) will be used in the ADA incidence tables:

1. PRE-AB NEG - TE ADA NEG
2. PRE-AB NEG - TE ADA POS
3. PRE-AB NEG - TE ADA INCONCLUSIVE
4. PRE-AB POS - TE ADA NEG
5. PRE-AB POS - TE ADA POS
6. PRE-AB POS - EQ
7. PRE-AB POS - TE ADA INCONCLUSIVE

8. MISSING
9. TOTAL PRE-AB NEG (equals 1 + 2 + 3)
10. TOTAL PRE-AB POS (equals 4 + 5 + 6 + 7)
11. TOTAL TE ADA NEG (equals 1 + 4)
12. TOTAL TE ADA POS (equals 2 + 5)
13. TOTAL TE INCONCLUSIVE (3 + 7)
14. TE POS within PRE-AB NEG POPULATION (equals 2/9)
15. TE POS within PRE-AB POS POPULATION (equals 5/10)

Incidences will be shown per treatment group. The number of subjects (s) in each subject category or derived set (excluding 14-15) is divided by the number of subjects (n) within each treatment group, excluding the subjects who are classified as missing. Incidences are shown as s/n (%), with the calculated percentage added in between brackets.

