#### **9.4.6 ADA and NAb incidence over time**

For ADA and NAb data, incidence of positive samples over time will be calculated. Positivity needs to be deducted based on reported titer values (ADA) or response ratio (NAb), as clarified in [Table 1](#). Incidence calculation should account for subject drop-out: for each visit, the number of positive samples is divided by the available results for the given visit (positive + negative samples (reported and/or imputed), excluding missing values (NA & NR)). The latter should be clarified in a footnote of the concerning tables.

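### Treatment-emergent ADA incidence keeps subjects with no post-dose result in its denominator, and NAb Table 5 does not settle whether such subjects are kept or excluded

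*SAP*

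**What the plan says.** **ADA classes (SAP 9.3.1, Table 2; Table 3 is the same for mADA).** MISSING is reserved for the case "No pre-dose samples are available". A subject whose pre-dose status is known but for whom "All post-dose samples(/results) are missing" is INCONCLUSIVE: class 3 if pre-dose negative, class 7 if pre-dose positive.

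**ADA incidence (SAP 9.4.1, repeated in 9.4.2 and 9.4.3).** The positive numerator is "TOTAL TE ADA POS (equals 2 + 5"). Percentages use the subjects in the treatment group, "excluding the subjects who are classified as missing". For mADA the base is first restricted to subjects characterised in that assay. The within-stratum rates are set 14 (class 2 over set 9) and set 15 (class 5 over set 10). Set 9 is "TOTAL PRE-AB NEG (equals 1 + 2 + 3") and set 10 is "TOTAL PRE-AB POS (equals 4 + 5 + 6 + 7"), so each contains its inconclusive class.

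**NAb (SAP 9.3.4, Table 5; 9.4.4).** The INCONCLUSIVE classes are defined as for ADA, but MISSING reads "No pre-dose (and/or post-dose) samples are available". Again only MISSING leaves the denominator.

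**Elsewhere in the SAP.** Section 4.3.1 leaves missing values out of percentage denominators. Section 9.4.6, on incidence by visit, divides by available results in order to allow for drop-out, "excluding missing values (NA & NR").

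**The concern.** A TE rate should be read as the share of subjects who developed antibodies among those in whom this could be seen. Classes 3 and 7 have no post-dose result, so they can never enter the numerator, yet they sit in the denominator of sets 11, 12, 14 and 15. Any such subject lowers the reported rate.

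The case can occur. The immunogenicity tables use the safety population (SAP 13.5), which requires only one dose (SAP 4.1.3). The first listed post-dose sample is at Week 12. Under Protocol 3.4.1.3, subjects who are lost to follow-up, withdraw consent or die have no Early Termination or Follow-up Visit. A subject who leaves in one of these ways before Week 12 contributes a dose but no post-dose sample.

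For NAb the problem is different. The class such a subject receives decides whether the subject is in the denominator, and Table 5 permits both answers. Two programmers could each follow the SAP and report different rates.

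**Working it through.** The plan states no immunogenicity rate, so there is no figure to reproduce. The check is on the denominator rule and on the class definitions.

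**1. Size of the ADA effect.** Let n be the non-missing subjects, k those in classes 3 and 7, and P those in classes 2 and 5.

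- SAP rate = P / n
- Evaluable rate = P / (n - k)
- Hence SAP rate = evaluable rate x (1 - k/n), a relative reduction of k/n.

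The value n = 501 is the planned maximum (SAP 3.2), used for scale only. The values of k and P are assumptions, with P chosen for an evaluable rate of about 20%.

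| k | P | SAP rate P/501 | Evaluable rate P/(501 - k) |
|---|---|---|---|
| 5 | 99 | 19.8% | 99/496 = 20.0% |
| 10 | 98 | 19.6% | 98/491 = 20.0% |
| 25 | 95 | 19.0% | 95/476 = 20.0% |
| 50 | 90 | 18.0% | 90/451 = 20.0% |

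Results are shown by parent-study arm (SAP 4.2.2). In an assumed group of 50 with 10 positives, the SAP rate is 20.0%. The evaluable rate is 10/48 = 20.8% with k = 2 and 10/45 = 22.2% with k = 5.

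**2. Within-stratum rates.** Take an invented split of 501 subjects, classes 1 to 7 = 300, 60, 15, 60, 20, 36, 10.

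- Set 12: 80/501 = 16.0% against 80/476 = 16.8%.
- Set 14: 60/375 = 16.0% against 60/360 = 16.7%.
- Set 15: 20/126 = 15.9% against 20/116 = 17.2%.

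**3. NAb classes.** Cross the pre-dose state (none, negative, positive) with the post-dose state (none, negative, positive) and apply Table 5.

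| Pre-dose | Post-dose | MISSING read with *or* | MISSING read with *and* only |
|---|---|---|---|
| none | none | MISSING | MISSING |
| none | negative or positive | MISSING | no class |
| negative | none | MISSING and NEG - INCONCLUSIVE | NEG - INCONCLUSIVE |
| positive | none | MISSING and POS - INCONCLUSIVE | POS - INCONCLUSIVE |
| negative or positive | negative or positive | one class | one class |

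The first reading makes classes overlap. The second leaves subjects with only post-dose samples unclassified. Neither gives classes that are both exclusive and exhaustive.

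With an assumed 40 NAb positives among 501 subjects, the reported rate is 40/501 = 7.98% if subjects without post-dose samples are INCONCLUSIVE. If they are MISSING, it is 40/476 = 8.40% with k = 25 and 40/451 = 8.87% with k = 50.

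**The case against.** The strongest defence is that this is a transparent classification table. On one denominator, classes 1 to 7 add to 100%. The SAP's immunogenicity endpoints are the subject classifications themselves (SAP 3.3), and no primary or secondary endpoint is defined. Every row is printed as a count over n, so a reader can rebuild the evaluable ADA rate. This stands. It limits the harm, but it does not make the printed TE percentage a rate among subjects who could be assessed.

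Several stronger inferences are tempting and are not supported:

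- *Inconclusive subjects are counted as negatives.* They are not. TOTAL TE ADA NEG is classes 1 + 4 only, and inconclusives have their own total (set 13). The negative percentage falls by the same factor as the positive one.
- *ADA incidence is ambiguous.* It is not. The Table 2 classes do not overlap; the ambiguity is confined to NAb.
- *NAb incidence is both diluted and undefined.* These are alternatives. Dilution arises only if the subjects are classed INCONCLUSIVE.
- *Section 9.4.6 directly contradicts 9.4.1.* The former counts samples at a visit and the latter classifies subjects, so they are different quantities. The comparison shows only that the SAP allows for drop-out in one and not in the other.
- *The shortfall is 5% or 10%.* No document gives k. Samples are scheduled every 12 weeks from Week 12, at Early Termination and at Follow-up, so few treated subjects should have none.
- *The evaluable rate is the true rate.* That would require early leavers to resemble the subjects who were sampled.

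**Conclusion.** The point holds in two separate parts.

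First, for ADA, mADA and overall incidence, the stated rule puts the TE rate below the evaluable-subject rate by the relative amount k/n. On the assumed range of 5 to 50 inconclusive subjects out of 501, that is 1% to 10% relative, or 0.2 to 2.0 percentage points at an evaluable rate of 20%. The likely overall effect is at the lower end, with more room for distortion in small parent-arm groups. The mADA base consists of subjects who already have a positive post-dose ADA sample, so an inconclusive mADA class arises there only when the mADA results themselves are missing.

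Second, NAb incidence has no unique denominator, because Table 5 places subjects without post-dose samples in two classes that 9.4.4 treats in opposite ways. Recomputing from the printed rows does not cure this, since the rows depend on the class chosen.

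The analysis is descriptive, so no error rate or power is affected. This is a minor point worth correcting.

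**What to change.** 1. **Table 5.** Define NAb MISSING as no pre-dose sample, as in Tables 2 and 3. Define INCONCLUSIVE as pre-dose status known with no post-dose result.
2. **Sections 9.4.1 to 9.4.3.** For sets 11, 12, 14 and 15, divide by subjects with a pre-dose status and at least one post-dose result. Set 14 becomes 2/(1 + 2) and set 15 becomes 5/(4 + 5 + 6). Equivocal subjects (class 6) stay in the denominator and keep their own row, so sets 11 and 12 and class 6 together make up the evaluable subjects.
3. **Section 9.4.4.** Do the same for NAb sets 10, 11, 13 and 14. Sets 10 and 11 use classes 1 to 4, set 13 becomes 2/(1 + 2) and set 14 becomes 4/(3 + 4).
4. Keep pre-dose prevalence on all subjects with pre-dose data, and report inconclusive subjects as a count.

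No new data are needed. The edits touch the denominator sentence in each of the four subsections, the set formulas and Table 5. The drawback is that one table then carries two denominators, so a footnote must say which rows use which.

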#### **9.4.2 *Incidence of mADA subject classes and derived sets***

The same subject categories (1-8) and derived sets (9-15) as shown above in [9.4.1](#) will be presented in the mADA incidence table, but the denominator to calculate incidences differs.

Incidences will be shown per treatment group. The number of subjects (s) in each subject category or derived set (excluding 14-15) is divided by the number of subjects (n) within each treatment group which were characterized in mADA assay (i.e. “PRE-AB POS – EQ” in ADA assay), excluding the subjects who are classified as missing. Incidences are shown as s/n (%), with the calculated percentage added in between brackets.

#### **9.4.3 *Incidence of overall subject classification (ADA, mADA results) and derived sets***

The following subject categories (1-8) and derived sets (9-13) will be used in the overall incidence tables:

1. PRE-AB NEG - TE ADA NEG
2. PRE-AB NEG - TE ADA POS
3. PRE-AB NEG - TE ADA INCONCLUSIVE
4. PRE-AB POS - TE ADA NEG
5. PRE-AB POS - TE ADA POS
6. PRE-AB POS - EQ
7. PRE-AB POS – TE ADA INCONCLUSIVE
8. MISSING
9. TOTAL PRE-AB NEG (equals 1 + 2 + 3)
10. TOTAL PRE-AB POS (equals 4 + 5 + 6 + 7)
11. TOTAL TE ADA NEG (equals 1 + 4)
12. TOTAL TE ADA POS (equals 2 + 5)
13. TOTAL TE INCONCLUSIVE (3 + 7)
14. TE POS within PRE-AB NEG POPULATION (equals 2/9)
15. TE POS within PRE-AB POS POPULATION (equals 5/10)

Incidences will be shown per treatment group. The number of subjects (s) in each subject category or derived set (excluding 14-15) is divided by the number of subjects (n) within each treatment group, excluding the subjects who are classified as missing. Incidences are shown as s/n (%), with the calculated percentage added in between brackets.

#### **9.4.4 Incidence of NAb subject classes and derived sets**

The following subject categories (1-7) and derived sets (8-14) will be used in the mADA incidence tables:

1. PRE-DOSE NEG - NEG ON TREATMENT
2. PRE-DOSE NEG - POS ON TREATMENT
3. PRE-DOSE POS - NEG ON TREATMENT
4. PRE-DOSE POS - POS ON TREATMENT
5. PRE-DOSE NEG - INCONCLUSIVE
6. PRE-DOSE POS - INCONCLUSIVE
7. MISSING
8. TOTAL PRE-DOSE NEG (equals 1 + 2 + 5)
9. TOTAL PRE-DOSE POS (equals 3 + 4 + 6)
10. TOTAL NEG ON TREATMENT (equals 1 + 3)
11. TOTAL POS ON TREATMENT (equals 2 + 4)
12. TOTAL INCONCLUSIVE (5 + 6)
13. POS ON TREATMENT within PRE-DOSE NEG POPULATION (equals 2/8)
14. POS ON TREATMENT within PRE-DOSE POS POPULATION (equals 4/9)

Incidences will be shown per treatment group. The number of subjects (s) in each subject category or derived set (excluding 13-14) is divided by the number of subjects (n) within each treatment group, excluding the subjects who are classified as missing. Incidences are shown as s/n (%), with the calculated percentage added in between brackets.

#### **9.4.5 Safety subgroup analysis**

For the following subgroups, the incidence rates will be determined of the different overall subject classifications (1-8) as listed in 9.4.3.

- Injection-site reaction
  - No injection-site reaction
  - At least 1 injection-site reaction
- Hypersensitivity reaction
  - No hypersensitivity reaction
  - At least 1 hypersensitivity reaction

#### **9.4.6 ADA and NAb incidence over time**

For ADA and NAb data, incidence of positive samples over time will be calculated. Positivity needs to be deducted based on reported titer values (ADA) or response ratio (NAb), as clarified in [Table 1](#). Incidence calculation should account for subject drop-out: for each visit, the number of positive samples is divided by the available results for the given visit (positive + negative samples (reported and/or imputed), excluding missing values (NA & NR)). The latter should be clarified in a footnote of the concerning tables.

## **10 INTERIM ANALYSES**

No interim analysis are foreseen.

## **11 CHANGE FROM ANALYSIS PLANNED IN PROTOCOL**

The subgroup analysis for efficacy according to the protocol included demographics (including weight and region), baseline disease characteristics, and baseline and prior medications, but will be limited to age category and geographic region.

A second sensitivity analysis will be done for efficacy based on NRI for the categorical endpoints analysed in the first sensitivity analysis.

The protocol mentions a subgroup analysis for safety which will not be performed.

The protocol states descriptive statistics will be used to summarize changes from baseline, but model-based, baseline-adjusted LS means and 95% CI will be used for efficacy endpoints.

## **12 CONVENTIONS**

### **12.1 Analysis Phases and Visit Windows**

#### ***12.1.1 Algorithm of allocating visits to time windows***

All assessments (including unscheduled assessments) will be placed into time windows according to their relative day (DY) in the study, according to the following allocation table:

Time point label	Target day	Interval lower bound	Interval upper bound
Week 4	29	1	43
Week 8	57	44	71
Week 12	85	72	126
Week 24	169	141	197
Week 36	253	225	281

Time point label	Target day	Interval lower bound	Interval upper bound
Week 48	337	309	365
Week 60	421	393	449
Week 72	505	477	533
Week 84	589	561	617
Week 96	673	645	700
Week 104	729	701	Week 102 visit date + 28 days
Follow-up		Last treatment date + 29 days	+INF

The definition of the time window for “Follow-up” implies that for Week 4 to Week 104 assessments, if the assessment or sample date is more than 28 days after the last dose of treatment, the assessment will be mapped to the Follow-up visit. If the assessment or sample date is less than or equal to 28 days after the last dose of treatment (including for assessments or samples taken at the early termination visit, if this condition holds), the assessment will be mapped to the corresponding analysis visit, in case it falls within the interval lower and upper bound for this analysis visit.

Baseline is defined in section 4.2.1.

Tables, figures and listings will present the time points as defined above, not the case report form (CRF) visits.

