## 3 STUDY DESIGN

### 3.1 Overall Study Design

This is a multicenter, open-label extension (OLE) phase II study of ALX-0061 administered s.c. in subjects with active RA who have completed the ALX-0061 treatment and assessment period of one of the preceding Phase IIb studies with ALX-0061 (C201 or C202) and who achieved at least 20% improvement in swollen joint count (SJC) and/or tender joint count (TJC) (66/68 counts) compared to baseline at the final visit of the preceding study and for the countries where there was approval for the study.

Eligible subjects will receive ALX-0061 150 mg s.c. injections, beginning at Day 1 (Week 0) of the OLE and every 2 weeks (q2w) thereafter up to and including Week 102. Eligible subjects from study ALX0061-C201 will also continue their methotrexate (MTX) treatment. Subjects will return for 12 ambulatory visits planned at Day 1 (Week 0), and Weeks 4, 8, 12, 24, 36, 48, 60, 72, 84, 96 and 104. Subjects who received study drug up to and including Week 102, should return for the End of Treatment Visit at Week 104 and for the Follow-up Visit 12 weeks after the last study drug administration at Week 102.

In the current OLE study, maintenance of the response will be reassessed at the study visits every 12 weeks from Week 12 until Week 96. Subjects who fail to maintain response and meet efficacy discontinuation criteria (< 20% improvement in both SJC and TJC

compared to baseline of the preceding Phase IIb study) will be discontinued from the study.

The schedule of assessments can be found in [Appendix 1: Schedule of assessments](#).

As this is an OLE study, blinding is not required.

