#### **Efficacy endpoints:**

- American College of Rheumatology (ACR) ACR20, ACR50, and ACR70 response rate over time (Week 0, Week 12, Week 24, Week 36, Week 48, Week 60, Week 72, Week 84, Week 96 and Week 104).
- Actual values in ACR-N index improvement over time (Week 0, Week 12, Week 24, Week 36, Week 48, Week 60, Week 72, Week 84, Week 96 and Week 104).
- Actual values and change from baseline values in Disease Activity Score using 28 joint counts (DAS28) using CRP and ESR, simplified disease activity index (SDAI) and clinical disease activity index (CDAI) over time (Week 0, Week 12, Week 24, Week 36, Week 48, Week 60, Week 72, Week 84, Week 96 and Week 104).
- Disease activity: response rate of remission and response rate of low disease activity (LDA) based on DAS28(ESR), SDAI, CDAI, Boolean (only remission) over time (Week 0, Week 12, Week 24, Week 36, Week 48, Week 60, Week 72, Week 84, Week 96 and Week 104).
- Disease activity: response rate of DAS28(CRP) < 2.6 and response rate of low disease activity (LDA) based on DAS28(CRP) over time (Week 0, Week 12, Week 24, Week 36, Week 48, Week 60, Week 72, Week 84, Week 96 and Week 104).
- Disease activity: rate of maintained remission at consecutive time points based on DAS28(ESR), SDAI, CDAI, Boolean and rate of maintained LDA at consecutive time points based on DAS28(ESR) over time (Week 0, Week 12, Week 24, Week 36, Week 48, Week 60, Week 72, Week 84, Week 96 and Week 104).
- Disease activity: rate of maintained DAS28(CRP) < 2.6 at consecutive time points and rate of maintained LDA at consecutive time points based on DAS28(CRP) over time (Week 0, Week 12, Week 24, Week 36, Week 48, Week 60, Week 72, Week 84, Week 96 and Week 104).

- European league against rheumatism (EULAR) DAS28 response rate (good, moderate, or no response) over time (Week 0, Week 12, Week 24, Week 36, Week 48, Week 60, Week 72, Week 84, Week 96 and Week 104).
- Actual values and change from baseline values in HAQ-DI over time (Week 0, Week 12, Week 24, Week 36, Week 48, Week 60, Week 72, Week 84, Week 96 and Week 104).
- HAQ-DI response rate (i.e., those who have a clinically meaningful improvement from baseline of  $\geq 0.25$  in HAQ-DI) and HAQ-DI normal physical function response rate (i.e., those who have a score of  $\leq 0.5$ ) over time (Week 0, Week 12, Week 24, Week 36, Week 48, Week 60, Week 72, Week 84, Week 96 and Week 104).

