### 4.2 Key Definitions and Labels

#### 4.2.1 *Definition of baseline and change from baseline*

The baseline value will be the baseline value of the parent study.

The absolute change from baseline will be calculated for all post-baseline time points as:  
Change from baseline at time point t = value at time point t – baseline value

For selected efficacy endpoints, the percentage change from baseline will be calculated for all post-baseline time points as: Percentage change from baseline at time point t =  $100 * (value at time point t - baseline value) / baseline value$ . As percentage change can not be calculated for subjects with a baseline value of 0, these subjects will not be included for the corresponding summary analysis (if planned) and the respective column(s) will be kept blank for the corresponding listing.

For the changes from baseline, only subjects with both a baseline value and a value at the post-baseline time point will be included.

Wherever in the document 'change from baseline' is mentioned, it concerns the absolute change from baseline.

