#### **4.2.5 *Visit Windows***

The visit windows as defined in Section 12.1 will be applied to all parameters.

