### **12.1.2 Selection of visits**

It is possible that more than one visit gets allocated into the same time window. In that case, only one visit will be selected for analysis tables and figures. The nonselected visit(s) will only be listed. In case an assessment gets allocated to a time window at which the assessment was not scheduled as per protocol, this assessment will not be shown in the tables or figures but will only be listed.

The visit with a DY closest to the target day will be selected. In case of ties on the same day with time not available, the assessment linked with the CRF visit will be selected for analysis.

In case more than one parameter is measured per time point (e.g. for lab), the selection is performed per parameter and per time point, not per “sample” and per time point. Missing values are removed before the selection is made.

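### The SAP visit-window table has no Week 0 row and opens Week 4 at Day 1, so the rule as written gives the required Week 0 results no time point of their own (minor correction)

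*SAP*

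**What the plan says.** SAP 12.1.1 sets the rule: "All assessments (including unscheduled assessments) will be placed into time windows according to their relative day (DY) in the study". The table that follows starts with Week 4 (target Day 29, Days 1 to 43), then Week 8 (target 57, Days 44 to 71) and Week 12 (target 85, Days 72 to 126), and runs on to Week 104 and Follow-up. There is no row for Week 0.

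The surrounding text leaves no exemption:

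- SAP 4.2.5: "The visit windows as defined in Section 12.1 will be applied to all parameters".
- SAP 12.1.1, last sentence: "Tables, figures and listings will present the time points as defined above, not the case report form (CRF) visits".
- SAP 12.1.1 refers the reader to 4.2.1 for baseline, and there "The baseline value will be the baseline value of the parent study".
- SAP 3.1 has dosing "beginning at Day 1 (Week 0) of the OLE".
- SAP 12.1.2 keeps the value closest to the target day after removing missing values. For an assessment that lands in a window where the protocol does not schedule it, "this assessment will not be shown in the tables or figures but will only be listed".

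The endpoints, however, call for Week 0. SAP 3.3 lists, for example, "ACR20, ACR50, and ACR70 response rate over time (Week 0, Week 12, Week 24" and onward to Week 104. SAP 9.1 wants Week 0 shown in every by-time-point immunogenicity display, in addition to the parent screening and baseline samples.

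**The concern.** A programmer who follows 12.1 literally cannot produce a Week 0 column. The pointer to 4.2.1 does not help, because that baseline belongs to the parent study, and SAP 9.1 treats it as distinct from Week 0. The CRF visit label cannot help either, because 12.1.1 rules it out for display.

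Three things are at stake:

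- Week 0 summaries that the SAP promises have no assigned time point. One of them is maintained remission at Week 0, which SAP 3.3 lists and which 12.3 defines through remission at that week and at all consecutive time points.
- A pre-dose value can be reported under an on-treatment label.
- It is not stated whether the LOCF analysis in SAP 6.2 may carry a Week 0 value forward. Two programmers could reasonably differ.

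**Working it through.** **1. Day numbering.** Section 12.1.1 does not define relative day. SAP 3.1 makes Day 1 the same as Week 0, and the AE onset-day formula in 12.4.1 (date minus first C203 dose date, plus 1) agrees. Check against the table: target day = 7 × week + 1 gives 29, 57, 85, 169, 253, 337, 421, 505, 589, 673 and 729 for Weeks 4, 8, 12, 24, 36, 48, 60, 72, 84, 96 and 104. All 11 stated targets are reproduced. The same formula gives Week 0 a target of 7 × 0 + 1 = Day 1, which lies inside the Week 4 interval of 1 to 43.

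**2. Where the Week 0 data fall.** Scheduling is taken from the protocol Schedule of Assessments. Laboratory timing is from footnote B (parent Week 22 or Week 10, two weeks before the parent Week 24 or Week 12 visit).

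| Week 0 data | Relative day | Row | Scheduled at Week 4? | Result under 12.1.2 |
|---|---|---|---|---|
| Joint counts, VAS scores, HAQ-DI | 1 | Week 4 | No | Listed only |
| PK, immunogenicity | 1 | Week 4 | No | Listed only |
| Vital signs | 1 | Week 4 | Yes | See step 3 |
| Routine laboratory, including CRP and ESR | about −14 | None | – | No time point |

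The laboratory result does not depend on the exact day: every day tested from −16 to −10 falls in no window. Days −4 and −1 also fall in no window, so a baseline visit held shortly before the first C203 dose would fare no better. CRP and ESR belong to the routine panel (footnote H), so Week 0 DAS28, SDAI and Boolean remission depend on this row too.

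**3. Vital signs.** A Week 4 visit within ±3 days is on Days 26 to 32, at most 3 days from the target of 29. Day 1 is 29 − 1 = 28 days away. If a Week 4 value exists, it is chosen and the Week 0 value drops out of the tables. If the Week 4 value is missing, the pre-dose Day 1 value is the nearest one left unless an unscheduled reading lies closer, and it is tabulated as Week 4.

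**4. What the SAP asks for.** Endpoint bullets in SAP 3.3: 13 efficacy + 1 PK + 2 immunogenicity + 5 safety = 21. Those naming Week 0: 13 + 1 + 0 + 4 = 18. This counts how often Week 0 is required. It does not measure the effect on results.

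**5. LOCF.** SAP 6.2 carries forward the last preceding post-baseline value. Week 0 comes after the parent baseline, so under 4.2.1 it is post-baseline. With no Week 0 time point in 12.1, nothing confirms that it is available to carry forward.

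**6. Check of the remedy.** With a Week 0 row and Week 4 starting at Day 2, Day 1 maps to Week 0 and Days 26 to 32 still map to Week 4.

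**The case against.** The best defence is that Week 0 data are imported from the parent study and the table was meant only for data collected after entry. Several places support this:

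- Protocol 3.4.1.2 says the parent Week 24 or Week 12 data serve the analysis.
- SAP Table 1, footnote 1, groups the OLE baseline visit with parent-trial data.
- Appendix 1, footnote B, names the laboratory source.
- Listing 16.2.10.1 shows a C203 baseline result separately, and SAP 12.3 refers to a Week 0 visit for MTX dose.
- The paragraph below the window table speaks of Week 4 to Week 104 assessments.

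This stands as evidence of intent, and it keeps the point small. It does not supply the rule: 12.1 claims all assessments and all parameters, and none of these passages assigns the data to a Week 0 time point or moves the Week 4 lower bound off Day 1.

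It is also fair to say that SAP 6.2 together with 4.2.1 arguably already admits Week 0 to LOCF. One sentence would settle it.

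A reader might infer that Week 0 is the reference against which maintenance of response is judged. The documents do not support this: response and every change are measured against the parent baseline (protocol 3.1.1 and 3.6.4; SAP 3.1 and 4.2.1).

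A reader might also infer that Weeks 4 and 8 carry no efficacy data, so that Week 0 is the only efficacy value for a subject who stops before Week 12. That is wrong as well. No joint-count, VAS or HAQ-DI assessment is scheduled at Weeks 4 and 8, but CRP and ESR are, and SAP 6.1 counts both as efficacy parameters. In addition, an Early Termination visit two weeks after a Week 10 dose falls on Day 85, inside the Week 12 window.

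**Conclusion.** The point holds as a minor correction. The allocation rule as written contradicts SAP 3.3 and 9.1: it leaves Day 1 joint-count, VAS, HAQ-DI, PK and immunogenicity values in the listings only, lets a pre-dose vital sign stand in for a missing Week 4 value, and gives the Week 0 laboratory values no window.

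A reader might infer that the Week 0 results will be lost. The documents do not show that. The data exist, their source is named, and a sensible programmer would probably recover the intended column. The protocol defines no primary endpoint (SAP 3.3), SAP 6.1 plans no inferential analysis, and Week 0 is not the reference for change or response.

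A reader might also take the days between the later windows for the same kind of defect. They are not: 12.1.1 maps a value only "in case it falls within the interval lower and upper bound for this analysis visit", and every scheduled visit from Week 4 on, at ±3 days, lies inside its window.

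The conclusion assumes that relative day counts from the first C203 dose as Day 1, and that parent Week 22 or 10 sampling is about 14 days earlier. The documents do not say how many subjects lack a Week 4 vital sign, so the extent of that substitution cannot be sized.

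**What to change.** In SAP 12.1.1, add a Week 0 row defined by visit rather than by relative day: the pre-dose OLE baseline visit, which is the parent Week 24 (C201) or Week 12 (C202) visit. Take the laboratory values from the source already named in Appendix 1, footnote B, and handle them consistently with the parent study's own Week 24 or Week 12 derivations, so that Week 0 DAS28 and related scores agree between the two reports. These documents do not show whether CRP or ESR was also sampled at the parent Week 24 or 12 visit, so this needs checking against the parent plans. Protocol exclusion 12g should not be borrowed as the fallback rule. It governs eligibility under 12a to 12e only, and those do not include CRP or ESR.

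Start the Week 4 window at Day 2. In SAP 6.2, state whether a Week 0 value may be carried forward by LOCF.

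The cost is one table row, one changed bound and one or two sentences. No new data are needed, and the mapping of scheduled Week 4 visits does not change.
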